8.2 EXCLUSION CRITERIA

The presence of any of the following will exclude the potential study participant from entry into the study:

- 1. Known hypersensitivity to any components of the Obagi 360 products.
- 2. Currently taking oral retinoids.
- 3. Use of any of the following in the preceding 6 months: any laser or IPL treatment, toxin, chemical peel, dermabrasion.
- 4. Use of any product which may cause irritation as per the judgment of the investigator
- 5. Use of topical retinoids in the preceding 3 months.
- 6. Use of Alpha or Beta hydroxy acids in the preceding month.
- 7. Significant history of eczema, atopic dermatitis, psoriasis in the facial area.
- 8. Any active facial inflammatory condition.
- 9. Female subject that is pregnant, breast feeding, or planning a pregnancy during the course of the study
- 10. History of poor cooperation, non-compliance or unreliability
- 11. The Investigator deems the subject an unsuitable candidate for this study

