- 12. No clinically significant abnormal findings based on the medical history including medication history that may affect study participation as determined by the Investigator
- 13. No recent history of drug or alcohol abuse

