10 CONCOMITANT MEDICATIONS

Medications in use at study entry should be documented on the CRF. Documentation should include medications that subjects take on an elective or as needed basis. If medications are related to a pre-existing (concomitant) condition or disease this condition or disease will be documented on the Medical History page of the CRF. In general, the addition of a concomitant medication upon or after treatment represents a new adverse event. Worsening of a condition present upon entry or noted as medical history also represents a new AE.

The following medications, preparations, and treatments are prohibited during the study as follows:

- 1. All topical skin care products on the face. Non-medicated facial cleansers are allowed. The use of Latisse is allowed. Makeup is allowed but must be removed for study visits.
- 2. All facial treatments including toxins, fillers, microdermabrasion, IPL, peels, facials, laser treatments, tightening treatments, and facial laser hair removal. Waxing and threading is allowed.
- 3. Oral or topical retinoids.
- 4. Alpha or beta hydroxy acids.

The use of other OTC and prescription medications, exclusive of the medications, preparations, and treatments listed above, are permitted after initiation of the study drug, but must be captured on the appropriate CRF page. If a patient uses any of the above prohibited treatments after initiation of the study drug, contact the medical monitor.

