14.2.3 ANALYSIS OF IMPROVEMENT IN PHOTODAMAGE BY INVESTIGATOR

For each of the components of the Investigator's Skin Grading Assessment for improvement in photodamage, the data will be summarized in the format shown in Table 4.

In the case of the Investigator's Assessments asked at each timepoint, a Paired T-Test will be used to compare the individual scores at each time point relative to their respective baselines for each treatment cell. The net change scores for each attribute will be shown as a distribution and converted to the number of subjects who showed "improvement", "stayed the same" or "worsened".

For all analyses unless otherwise specified, a two tailed p < 0.05 will be taken as the level of significance.

Table 4 Format for Summary of Investigator's Skin Grading Scale

Investigator's Skin Grading Skin Grading Component (e.g., Sallowness)

	Mean ± S.D.	P-value					
Baseline							
Day 14							
Day 28							
Day 56							
Day 84							
Net Change from Baseline							

Day 14	
Day 28	
Day 56	
Day 84	

Distribution of (Net Change) Scores

	-4	-3	-2	-1	0	+1	+2	+3	+4
Day 14									
Day 28									
Day 56									
Day 84									
	Two		d				7	X/orac	^

	ımprovea	=	vvorse
Day 14			
Day 28			
Day 56			
Day 84			

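### Oral retinoids exclude only if currently taken, while topical retinoids carry a 3-month look-back, so a subject who has just stopped an oral retinoid passes every fixed entry criterion

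*Protocol*

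**What the plan says.** Protocol Section 8.2 has two retinoid rules. Exclusion 2 is "Currently taking oral retinoids"; exclusion 5 is "Use of topical retinoids in the preceding 3 months". The exclusion list in the synopsis (Section 2) repeats both.

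The neighbouring criteria on specific earlier treatments also carry windows: "Use of any of the following in the preceding 6 months: any laser or IPL treatment, toxin, chemical peel, dermabrasion" (exclusion 3) and "Use of Alpha or Beta hydroxy acids in the preceding month" (exclusion 6).

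Section 10 lists "Oral or topical retinoids" among its banned items, under the lead-in "The following medications, preparations, and treatments are prohibited during the study as follows".

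Three further criteria could reach a recent oral user, all through judgment: inclusion 12, on "medication history that may affect study participation as determined by the Investigator"; exclusion 4, on irritating products; and exclusion 11, on general unsuitability.

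For efficacy, Section 14.2.3 states that "a Paired T-Test will be used to compare the individual scores at each time point relative to their respective baselines".

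**The concern.** For one drug class, the entry rule depends on the route. A subject who last used a topical retinoid 80 days before baseline is excluded; one who stopped an oral retinoid the day before is not. The protocol gives no reason for the difference, and Section 10 treats the two routes alike once the study has started.

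The design makes this matter more than it otherwise would. The test product contains 0.5% retinol, there is no reference arm, and efficacy is each subject's change from her own baseline. If an oral retinoid still acts on the skin at baseline, or its effect fades over the following 12 weeks, the resulting change in a component such as breakouts or texture cannot be told apart from the product's effect. Continuing benefit would favour the product and fading benefit would count against it, so the direction is unknown.

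The descriptive tolerability grades (Section 12.2) could be affected too. Table 1 schedules no tolerability assessment at baseline against which to recognise a pre-existing effect.

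**Working it through.** **Step 1. Compare the fixed rules.** Time off treatment required before baseline:

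| Prior treatment | Criterion (Section 8.2) | Look-back |
|---|---|---|
| Laser, IPL, toxin, peel, dermabrasion | Exclusion 3 | 6 months |
| Topical retinoids | Exclusion 5 | 3 months |
| Alpha or beta hydroxy acids | Exclusion 6 | 1 month |
| Oral retinoids | Exclusion 2 | none; current use only |

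Of these specifically named treatments, only oral retinoids have no look-back.

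**Step 2. Look for another rule that closes the gap.**

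- Section 10 applies during the study and sets no pre-study interval.
- Eligibility review, baseline grading and dispensing all take place at Visit 1 (Section 13.1), and the first application comes at the end of that visit (text following Section 7.4). No washout is built in.
- Inclusion 12 and exclusions 4 and 11 rest on the investigator's judgment. None names retinoids or a time window.
- Section 14.1 has prior medications summarised, so recent use may be visible in the report, but the subject stays in the analysis.

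No fixed criterion therefore excludes the subject who has just stopped.

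**Step 3. Size the possible effect.** The protocol gives 40 subjects (Section 14.3) and a two-tailed 5% level (Section 14.2.3). It gives no SD and no count of recent oral users. Assumptions: change SD 0.8 in unaffected subjects, normally distributed changes, no product effect, and *k* recent users who all drift *d* grades in the same direction on the 0–6 scale.

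- Shift in mean change = *k* × *d* / 40
- SE with the SD held at 0.8 = 0.8 / √40 = 0.126
- SD including the affected subjects = √(0.64 + *p*(1 − *p*)*d*²), with *p* = *k*/40; this SD divided by √40 gives the second SE
- Rejection rate: two-sided 5% paired t-test, 200,000 simulated trials

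| *k* | *d* | Shift | Shift in SE (SD 0.8) | SD with affected | SE | Shift in SE | Rejection rate |
|---|---|---|---|---|---|---|---|
| 0 | – | 0 | 0 | 0.800 | 0.126 | 0 | 0.050 |
| 1 | 1 | 1×1/40 = 0.025 | 0.20 | 0.815 | 0.129 | 0.19 | 0.049 |
| 2 | 1 | 2×1/40 = 0.05 | 0.40 | 0.829 | 0.131 | 0.38 | 0.058 |
| 4 | 1 | 4×1/40 = 0.10 | 0.79 | 0.854 | 0.135 | 0.74 | 0.095 |
| 4 | 2 | 4×2/40 = 0.20 | 1.58 | 1.000 | 0.158 | 1.26 | 0.18 |

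Example for the last row: *p* = 4/40 = 0.1, so SD = √(0.64 + 0.1 × 0.9 × 4) = √1.00 = 1.00.

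Drifts in opposite directions cancel in the mean.

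**The case against.** The strongest reply is that nothing here is contradicted. The synopsis and Section 8.2 agree, look-backs already differ by type of exposure, and nothing requires the two retinoid routes to share a window. The protocol also says nothing about how long an oral retinoid acts on facial skin. The topical window concerns a product applied to the skin being graded, so extending it to oral use is an inference. All of this is fair. The point is that a rule is set badly, not that two passages conflict, and carry-over is an assumption.

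The second reply is that a subject who stopped the day before baseline is an obvious case for inclusion 12 or exclusion 11, and that individual review is practical with about 40 subjects at no more than two centres. That reduces the risk without removing it: two investigators may decide differently, and the same clauses did not stop the sponsor fixing a window for the topical route.

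The third reply is about consequence. Visible inflation of the error rate needs about four recent oral users, 10% of the sample, all drifting the same way; the 0.18 figure also needs two full grades each. Nothing in the protocol suggests even one such subject. An open-label single-arm study cannot firmly attribute change to the product in any case. This stands, and it is why the point ranks low. It does not justify admitting an avoidable source of drift that the sponsor already guards against for the other route.

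**Conclusion.** The concern holds as a minor point. On the text it is certain: current use is the only fixed bar to oral retinoids at entry, while the topical route requires 3 months off.

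The effect on the results is conditional. It requires recent oral users to be enrolled, the investigators not to exclude them, and a residual or fading effect that moves the scores within 12 weeks. Under the assumptions shown, one user is negligible and two take the error rate only to about 0.058. The four-user, two-grade case is an upper bound and deserves little weight. The direction of any bias cannot be stated.

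An unseen statistical analysis plan would not change this, because eligibility is fixed in the protocol.

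**What to change.** In Section 8.2 and in the synopsis, reword exclusion 2 to: *Use of oral retinoids currently or in the preceding 3 months*. This borrows the sponsor's own topical window as a minimum. The protocol supports no specific longer figure, but the sponsor may set one on clinical grounds.

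The cost is one criterion edited in two places and possibly a few more screen failures. Visits, assessments and analysis are unchanged.

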8.3 STUDY SITES/SOURCE OF STUDY SUBJECTS

A sufficient number of subjects will be screened in order to enroll 40 subjects to the study. Up to two centers in the United States will be involved in the study. Enrollment will be stopped at all centers when the enrollment goal of 40 subjects has been reached.

8.4 STUDY SUBJECT IDENTIFICATION

Study subjects will be identified by a 3-digit site number (YYY) and a 3-digit subject number (XXX) as follows: YYY-XXX. Subject initials will be recorded as well (AAA). If the subject

CONFIDENTIAL AND PROPRIETARY INFORMATION OF OMP, INC.

does not have a middle initial, a hyphen will be used as a substitute (e.g., A-A). Subject confidentiality will be maintained by use of this method of study subject identification.

8.5 STUDY SUBJECT WITHDRAWAL OR EARLY TERMINATION

8.5.1 WITHDRAWAL/EARLY TERMINATION

An early termination occurs when an enrolled subject ceases participation in the study, prior to completing the protocol. Subjects must be permitted to withdraw from the study at any time for any reason. Subjects may be withdrawn at any time at the discretion of the investigator or sponsor for safety, compliance, or other reasons. In general, subjects should not be withdrawn by investigators prior to completion of the study unless there is documentation of any of the following:

- The investigator believes that the subject has experienced significant or disabling treatment-related adverse events (AEs) that can be diminished or avoided by subject withdrawal. Discussion with Obagi prior to withdrawal is preferred.
- Subject withdrawal is in the best interest of the health of the subject. A withdrawal for medical reasons should document the specific condition for removing the subject.
 Discussion with Obagi prior to withdrawal is preferred.
- Lost to follow-up.
- Death.

The final safety evaluation required by the protocol will be performed at the time of the early termination, if possible. All subject withdrawals will be fully documented.

Subjects who discontinue prematurely from the study will not be replaced until approved by the sponsor.

8.5.2 SCREEN FAILURES

A screen failure is a subject that is withdrawn from the study for any reason, after signing an Informed Consent Form without being enrolled. The Informed Consent Form signed by the subject should be kept with the source documents for subjects who do not pass the screening procedures. The documentation should include identification of the eligibility criterion or criteria that were and were not met. The subject should not be re-screened for this study without Obagi's approval.

9 TREATMENTS AND STUDY PRODUCTS

9.1 PRODUCT IDENTITY AND TREATMENTS ADMINISTERED

Obagi 360 contains: Obagi Exfoliating Cleanser, Obagi 0.5% retinol, and Hydrafactor SPF30. When used together under the guidance of a dermatologist/physician, these products are anticipated to work synergistically to provide improvement in the appearance of photodamage, fine lines, and wrinkles.

The Exfoliating Cleanser with maltodextrin (and) Eperua Falcata Bark Extract (Appendix 4) is intended to gently exfoliate the skin in preparation for the moisturizing retinol cream. The 0.5% retinol (in both the Moisturizer and the Night Cream; Appendix 5) is intended to improve skin texture and evens out roughness. For protection, the Hydrafactor SPF30 (Appendix 6), is a physical sunblock used as part of the Moisturizer.

9.2 CLINICAL SUPPLIES

Obagi or its designee will supply the Obagi 360 system to the sites.

9.2.1 PACKAGING AND LABELING

The packaging will be clearly labeled with the following information: study number, unique treatment number, contents, and storage instructions. Coordinators will write date dispensed, bottle #, and subject identification information on each package.

Sufficient drug supplies will be packaged and labeled. Kits will be assigned to qualified subjects at the baseline (Day 0) visit. Additional supplies will be sent to the study centers as necessary until the enrollment goal is met.

9.2.2 DISPENSING

The principal investigator or appropriate designee at each site will be responsible for dispensing the Obagi 360 system to the subjects. At baseline, Day 28 and Day 56 visits, the subject will receive a new Obagi 360 system for the following month's use. At the Day 28, 56 and 84 visits, the subject will return the unused portion of the previous month's supply to the site.

9.2.3 STORAGE

All products should be stored at room temperature 15° to 30°C (59° to 86°F). Protect from freezing. Each investigator will keep study drugs in a pharmacy or a locked and secured storage facility, accessible only to those individuals authorized by the investigator to dispense this study product.

9.3 ACCOUNTABILITY

The product will be released to the investigator/pharmacy after approvals of the study protocol have been received by Obagi from the IRB. Product accountability must be maintained for used product as well as the unused product. The principal investigator is responsible for ensuring that accurate records of the receipt of all investigational products are maintained, including date and amount received. Dispensing records of all investigational products will also be maintained including the date, amount dispensed, and the subject receiving the investigational products. All remaining investigational products must be returned to Obagi or its designee or destroyed immediately after the study is completed. Products deliberately and/or accidentally destroyed at shipment or at a study site should be accounted for and documented. The study products must not be used outside the study. All clinical supplies must be accounted for at the termination of the study and a written explanation provided for discrepancies.

9.4 DOSE ADMINISTRATION

The site will provide instructions for the proper application of Obagi 360 system at baseline (Appendix 1). Study product should be applied by the subject for the subsequent days. The subject will be instructed to use the Exfoliating Cleanser in the morning and in the evening. After the Exfoliating Cleanser is used in the morning, the Moisturizing Cream (0.5% retinol with moisturizers and Hydrafactor SPF 30) will be applied. After the Exfoliating Cleanser is used in the evening, the Night Cream (0.5% retinol with moisturizers) will be applied.

Written instructions for the proper administration of study product will be provided to the subject (Appendix 1).

9.5 STUDY RESTRICTIONS

Subjects will be instructed to refrain from use of certain concomitant treatments and medications during the study (Section 10).

9.6 ASSESSMENT OF TREATMENT COMPLIANCE

The subjects will return to for follow up on Day 14, 28, 56, and 84 to ensure compliance to protocol procedures, including refraining from the use prohibited concomitant treatments or medications.

10 CONCOMITANT MEDICATIONS

Medications in use at study entry should be documented on the CRF. Documentation should include medications that subjects take on an elective or as needed basis. If medications are related to a pre-existing (concomitant) condition or disease this condition or disease will be documented on the Medical History page of the CRF. In general, the addition of a concomitant medication upon or after treatment represents a new adverse event. Worsening of a condition present upon entry or noted as medical history also represents a new AE.

The following medications, preparations, and treatments are prohibited during the study as follows:

- 1. All topical skin care products on the face. Non-medicated facial cleansers are allowed. The use of Latisse is allowed. Makeup is allowed but must be removed for study visits.
- 2. All facial treatments including toxins, fillers, microdermabrasion, IPL, peels, facials, laser treatments, tightening treatments, and facial laser hair removal. Waxing and threading is allowed.
- 3. Oral or topical retinoids.
- 4. Alpha or beta hydroxy acids.

The use of other OTC and prescription medications, exclusive of the medications, preparations, and treatments listed above, are permitted after initiation of the study drug, but must be captured on the appropriate CRF page. If a patient uses any of the above prohibited treatments after initiation of the study drug, contact the medical monitor.

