12 SAFETY EVALUATIONS

12.1 SAFETY ASSESSMENTS – ADVERSE EVENTS (AE)

An AE is any untoward medical occurrence in a subject or clinical investigation subject administered a study product and which does not necessarily have a causal relationship with the study product. An AE can therefore be any unfavorable and unintended sign (including a clinically significant abnormal laboratory finding), symptom, or disease temporally associated with the use of an investigational or marketed study product, whether or not considered related to the investigational or marketed study product.

AEs include any illness, sign, symptom, or out-of-range AND clinically significant laboratory finding that has appeared or worsened during the course of the clinical study, regardless of causal relationship to the study product(s). The collection of non-serious AE information should begin at initiation of study product. Serious AEs (SAEs) should be collected from the time that the subject provides informed consent, which is obtained prior to the subject's participation in the clinical study, i.e., prior to undergoing any study-related procedure and/or receiving investigational product, through and including 30 calendar days after the last administration of the investigational product. Any SAE occurring after study completion must be promptly reported if a causal relationship to investigational product is suspected.

An evaluation of adverse experiences will be performed at each visit. The subject will be questioned to determine if any adverse events have been experienced since the last visit. All adverse events, regardless of perceived relationship to investigational product, will be reported and recorded on the appropriate case report forms. Any significant new abnormality will be recorded and followed until the abnormal finding returns to normal for that subject.

When a concomitant medication/therapy is reported during the study that is not related to medical history, a corresponding Adverse Event form will be completed and the reason for the treatment documented.

When a drug-related adverse event persists at the end of the study, the investigator will conduct follow-up contacts with the subject until the investigator/sponsor agree the event is satisfactorily resolved and/or stabilized.

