13.1 VISIT 1/BASELINE VISIT (STUDY DAY 0)

The following pre-study screening procedures should be completed prior to initiating study treatment:

- 1. Obtain a signed and dated subject informed consent form and authorization to use and disclose medical information prior to performing any study-specific procedures;
- 2. Obtain a signed and dated Photographic Release Form prior to obtaining any photographs
- 3. Collect demographic information including date of birth, sex, race, ethnicity and Fitzpatrick skin type;
- 4. Collect a medical history (only relevant, current/ongoing diseases/conditions and past surgeries/procedures as determined by the investigator);
- 5. Review inclusion and exclusion criteria;
- 6. Upon qualifying for the study, subjects will be assigned a study number (See Section 8.4);
- 7. Conduct Investigator's Skin Grading Assessment, see Section 11.1;
- 8. Obtain photographs. For details instruction on obtaining photographs, see Section 11.2;
- 9. A urine pregnancy test will be performed on females of child-bearing potential.
- 10. Review and record concomitant medications;
- 11. Dispense study product. Complete the product accountability CRF form;
- 12. Instruct subject in the application of the Obagi 360 system and provide written instructions;
- 13. Schedule the next visit with the subject on study Day 14 (\pm 2 days).

13.2 VISITS 2 THROUGH 5 (STUDY DAY 14 [\pm 2 DAYS], AND STUDY DAYS 28, 56, AND 84 [\pm 5 DAYS])

The following procedures will be performed at these visits:

- 1. Conduct Investigator's Skin Grading Assessment, see Section 11.1;
- 2. Obtain photographs. For details instruction on obtaining photographs, see Section 11.2;
- 3. A urine pregnancy test will be performed on females of child-bearing potential at the End of Study Visit.
- 4. Conduct subjects' self-assessment see Section 11.3, Appendix 2 and Appendix 3;
- 5. Assess tolerability of the Obagi 360 system;
- 6. Review and record concomitant medications;
- 7. Review and record adverse events:
- 8. Dispense/collect study product. Complete the product accountability CRF form;
- 9. Review with subject the application of the Obagi 360 system;
- 10. Schedule the next visit with the subject or end subject participation at Visit 5.

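### Two collection rules make a newly reported medication an adverse event without requiring that anything untoward happened, which pushes all-causality TEAE incidence upward

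*Protocol*

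**What the plan says.** Section 10 (Concomitant Medications) states: "In general, the addition of a concomitant medication upon or after treatment represents a new adverse event". The next sentence adds worsening of an existing condition as a further trigger. The same section lets subjects start other medicines, which must be recorded on the CRF: "The use of other OTC and prescription medications, exclusive of the medications, preparations, and treatments listed above, are permitted".

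Section 12.1 contains a second rule: "When a concomitant medication/therapy is reported during the study that is not related to medical history, a corresponding Adverse Event form will be completed", with the reason for treatment also recorded.

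The AE definition, also in Section 12.1, is narrower: "An AE is any untoward medical occurrence in a subject or clinical investigation subject administered a study product". It continues: "AEs include any illness, sign, symptom, or out-of-range AND clinically significant laboratory finding that has appeared or worsened during the course of the clinical study". Starting a medication is not on that list.

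Two places determine what counts as medical history. Section 10 sends the condition behind any medicine in use at entry, including elective and as-needed ones, to the Medical History page. Section 13.1 limits the history taken at baseline to "only relevant, current/ongoing diseases/conditions and past surgeries/procedures as determined by the investigator".

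Section 14.2.5.1 treats every AE with onset from the start of product to the end of study as treatment-emergent. It counts each subject once per rate and has no step that removes entries made only because a medication was started.

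**The concern.** An AE collection rule should capture events. These two rules capture medication starts as well, although a vaccination or a vitamin need not reflect anything that appeared or worsened. The reported TEAE incidence then depends partly on how often subjects start unrelated medicines, and partly on how fully the investigator lists medical history and which section a site follows.

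The study has one arm, so no control rate shows how much of the incidence comes from the rule. Such entries are also awkward to complete. The lowest severity grade in Section 12.1.1 presupposes a sign or symptom, and there is none to grade. This belongs to the protocol rather than to a statistical analysis plan: once a non-event has been recorded as an AE, removing it at analysis would be a post hoc exclusion.

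**Working it through.** **Step 1: apply the passages to concrete cases.**

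| Case | Meets AE definition (12.1)? | Section 10 rule | Section 12.1 form rule |
|---|---|---|---|
| Preventive vaccination during the study | No | AE, in general | Form required |
| New vitamin or supplement, no complaint | No | AE, in general | Form required |
| Medicine first reported on study, unchanged condition not in medical history | No | AE, in general, if it is an addition | Form required |
| Medicine newly added for a listed, unchanged condition | No | AE, in general | No form (exempt) |
| Usual medicine in use and documented at entry | No | Not an addition | No form (condition is listed) |

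In the first three rows the form rule conflicts with the definition. In the fourth the two rules differ from each other. In the fifth there is no problem.

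**Step 2: follow the entry into the tables.** An AE recorded after first use meets the TEAE definition in Section 14.2.5.1. It enters the overall incidence and the system organ class and preferred term tables.

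**Step 3: size.** The protocol states no AE rate and no rate of medication starts, so there is no figure of its own to reproduce.

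- Input from the protocol: N = 40 (Section 14.3), single arm. I take all 40 as the safety population.
- Effect per subject: one subject counted only because of a medication, with no other TEAE, adds 1/40 = 2.5 percentage points.
- Assumptions, for illustration: p = true share of subjects with a TEAE, 10% to 30%; q = share who start a medication with no untoward occurrence, 5% to 20%; p and q independent.
- Formula: reported incidence = 1 − (1 − p)(1 − q), so the rise is q(1 − p).

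For p = 20% and q = 5%: 1 − 0.80 × 0.95 = 0.24. For q = 20%: 1 − 0.80 × 0.80 = 0.36.

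| True p | q = 5% | q = 10% | q = 20% |
|---|---|---|---|
| 10% (4 of 40) | 14.5% | 19% | 28% |
| 20% (8 of 40) | 24% | 28% | 36% |
| 30% (12 of 40) | 33.5% | 37% | 44% |

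The rise runs from 3.5 points (p = 30%, q = 5%) to 18 points (p = 10%, q = 20%). At p = 20% the expected count goes from 8 to between 9.6 and 14.4 subjects. If medication starters tend to be the subjects who also have true AEs, the rise is smaller. Under the literal reading the overall incidence cannot fall.

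**The case against.** The best defence is that both sentences are meant as prompts. Section 10 is hedged, so it leaves room for medication starts with no event behind them. Section 12.1 asks for the reason for treatment, which points to looking for an underlying event. An investigator who applies the AE definition first would not report a vaccine, and the data queries in Section 14.5 might catch some entries. This softens Section 10. It does not remove the Section 12.1 rule, which is unhedged and whose only exemption is medical history.

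A reader might infer several stronger points that the protocol does not support:

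- *That usual medicines for chronic conditions routinely become AEs.* Section 10 requires the condition behind a medicine in use at entry, even an as-needed one, to be listed, so the Section 12.1 exemption applies. Only a medicine first reported on study for an unlisted condition is caught.
- *That the two rules contradict each other throughout.* A documented usual medicine is not an addition. The mismatch is confined to a medicine newly added for a listed, unchanged condition.
- *That treatment-related AE rates are inflated.* Section 12.1.2 requires an alternative cause for a judgement of not related. The recorded reason for treatment can usually supply one, so these rates should move little.
- *That incidence could double or triple.* For an assumed true 20%, that would need a quarter to a half of subjects to start such medicines, since (0.40 − 0.20)/0.80 = 0.25 and (0.60 − 0.20)/0.80 = 0.50. Nothing in the protocol suggests this. Inclusion criteria 11 and 12 point the other way: contraceptives must be stable, and there must be no clinically significant history findings.

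It is also fair that the AE analysis is descriptive, with no test or threshold, and that the error is toward over-reporting.

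**Conclusion.** The point holds as a defect of low severity in the AE collection wording. Section 12.1 requires, and Section 10 presumes, an AE where the protocol's own definition may not be met, and Section 14.2.5.1 then counts it. The direction is upward for all-causality TEAE incidence and the associated organ-class and preferred-term tables.

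The only size that follows from the protocol is 2.5 percentage points per affected subject, with 40 in the denominator. The range of 24% to 36% for a true 20% rests on an assumed 5% to 20% of subjects starting such a medication, on independence from true AEs, and on sites following the rules literally. Tolerability grading and the efficacy analysis are untouched.

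**What to change.** In Sections 10 and 12.1, replace both rules with one text, for example:

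> When a medication or therapy is added or first reported during the study, record its indication and ask whether an adverse event led to its use. Complete an AE form only if the AE (or SAE) definition in Section 12.1 is met. Preventive or elective use, and treatment of a pre-existing condition that has not worsened, whether or not listed in medical history, are recorded on the concomitant medication page only.

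This keeps the useful part of the current rules, which is that a new medication triggers a question about an event. Referring to the Section 12.1 definition, rather than to events after the start of product, keeps the text consistent with SAE collection from consent.

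The cost is a short change to two protocol sections and a matching line in the CRF instructions. Sites record slightly more indications, but Section 12.1 already asks for the reason for treatment.
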